
NAME OF COMPANY	NAME OF DRUG PRODUCT
HanAll Pharmaceutical International Inc. [name]	Tanfanercept ophthalmic solution 0.25% for treatment of Dry Eye Disease

Secondary Efficacy Analyses:
 
The continuous and ordinal secondary efficacy variables collected at each visit will be summarized descriptively (n, mean, standard deviation, median, min and max), and analyzed with two-sample t-tests and MMRM comparing each of the active treatment groups to placebo. All visit-based data will be analyzed at each visit. Changes from baseline at each post-baseline visit will be analyzed using MMRM with terms for baseline, visit (as a categorical term), treatment group and the interaction of visit and treatment group as fixed effects with correlated errors. No imputation will be performed for secondary efficacy variables. Secondary efficacy variables will be analyzed using the ITT population with observed data only unless otherwise specified in the Statistical Analysis Plan.
	

Safety Variables:
 
Adverse events (AEs) will be coded using the Medical Dictionary for Regulatory Authorities (MedDRA). Frequencies and percentages of subjects with treatment-emergent adverse events (TEAEs), serious TEAEs, and TEAEs causing premature discontinuation will be provided by treatment group. An AE is treatment emergent if it occurs or worsens after the first dose of study treatment. Furthermore, frequencies will be given of subjects with TEAEs by system organ class, by system organ class and preferred term, by system organ class, preferred term and maximal severity, by system organ class, preferred term and strongest relationship, and by system organ class, preferred term, maximal severity, and strongest relationship. Separate analyses will be performed for ocular specific and all AEs (including systemic).
 
Other safety endpoints including visual acuity, slit-lamp biomicroscopy, dilated fundoscopy, and intraocular pressure will be summarized by treatment group and visit using descriptive statistics. Changes or shifts from baseline will also be summarized where appropriate. For assessments performed by eye, study eye and fellow eye will be summarized separately. In addition, shifts from baseline to worst on-treatment value for ocular safety assessments will be summarized.
	

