8.4 Examination Procedures

An ICF must be signed and dated by the subject, the principal investigator (PI) or designee and witness (if required) before any study-related procedures are performed.

Procedures listed below should be performed in the given order. See [Appendix 3](#): Examination Procedures, Tests, Equipment, and Techniques for details on methodologies and grading systems.

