8.4.3 Visit 2: Day 1 – Confirmation and Baseline

- Placebo Collection: All used/unused placebo ampoules dispensed for Days –14 to 1 should be collected and reviewed by a trained study technician.
- Site staff must confirm subjects have NOT administered their morning placebo dose at home. If subject dosed prior to the visit, study visit procedures should begin 4 hours after time of dosing.
- Monitoring and Query of AEs: Report any AEs that occur after signing the ICF.
- Record all Changes in Concomitant Medications
- Ora Calibra® Ocular Discomfort Scale
- Ora Calibra® Ocular Discomfort & 4-Symptom Questionnaire
- VAS
- OSDI®
- BCVA Utilizing an ETDRS Chart
- Slit-Lamp Biomicroscopy
- Conjunctival Redness
- TFBUT
- Corneal and Conjunctival Staining (fluorescein)
- Corneal and Conjunctival Staining (lissamine green)
- Schirmer's Test

- Review of Inclusion and Exclusion Criteria

- Report a score of █ according to the Ora Calibra® Ocular Discomfort & 4-Symptom Questionnaire in at least one of the dry eye symptoms at Visits 1 and 2
- *Eligible subjects must have a positive response in at least one eye. A positive response is defined as meeting ALL of the following criteria in the same eye:*
 - Report a score of █ according to the Ora Calibra® Ocular Discomfort & 4-Symptom Questionnaire in at least one of the dry eye symptoms at Visit 1 and 2
 - Have a Schirmer's Test score of ≤ 10 mm and ≥ 1 mm in at least one eye at Visits 1 and 2
 - Have a corneal fluorescein staining score █ according to the Ora Calibra® Corneal and Conjunctival Staining Scale for Grading of Fluorescein Staining in at least one of the corneal regions █ in at least one eye at Visits 1 and 2
 - Have a CCSS of █ according to the Ora Calibra® Corneal and Conjunctival Staining Scale for Grading of Fluorescein Staining in at least one eye at Visit 2
 - Have a CCSS at Visit █ to CCSS at Visit 1
 - Have a conjunctival redness score █ according to the Ora Calibra® Conjunctival Redness for Dry Eye Scale in at least one eye at Visits 1 and 2
 - Have at least one eye, the same eye, satisfy all inclusion criteria for 8, 9, 10, 11, 12 and 13

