- Note: If only one eye qualifies then the single qualifying eye will be the study eye. In the case that both eyes are eligible for analysis, the study eye will be the eye with worse (higher) central corneal fluorescein staining at Visit 2. If the central corneal fluorescein staining is the equivalent in both eyes, then the right eye will be selected as the study eye.
- **Randomization** – subjects will be randomized according to the following two strata:
 1. Visit 2 study eye CCSS █ and
 2. Visit 1 CCSS minus Visit 2 CCSS (V1 CCSS - V2 CCSS); difference in study eye CCSS █
- **Blood Sampling** Blood samples will be collected from all subjects for immunogenicity testing █

- Study Drug Instillation at the Study Site All subjects meeting all other screening eligibility criteria after Visit 2 will be randomized to one of two treatment arms. Randomized subjects will self-administer their initial study drug dose bilaterally at the study site.
- Ora Calibra® Drop Comfort Assessments The Ora Calibra® Drop Comfort Scale will be performed immediately after instillation and then at 1, 2, and 3 minutes following instillation.
- Monitoring and Query of AEs
- Study Drug Dispensation Prior to discharge from the study site on Visit 2 (Day 1), randomized subjects will be educated in the self-administration of study drug. The initial, self-administered dose taken in-office at Visit 2 will be counted as a morning dose regardless of visit time, and subjects will be instructed to administer an evening dose that night. Subjects will receive their assigned study drug kit with sufficient supply to last until Visit 3 and will be instructed NOT to self-administer study drug on the morning of their next scheduled study visit (Visit 3, Day 8).
- Schedule Next Visit Subjects will be scheduled for Visit 3.

8.4.4 Visit 3: Day 8 ± 1 –Week 1

- Study Drug Collection All used/unused study drug vials dispensed for Days 1 to 8 should be collected and reviewed by a trained study technician.
- Site staff must confirm that subjects have NOT administered their morning study drug dose at home. If subject dosed prior to the visit, study visit procedures should begin 4 hours after time of dosing.
- Monitoring and Query AEs
- Recording of all Changes in Concomitant Medications
- Ora Calibra® Ocular Discomfort Scale
- Ora Calibra® Ocular Discomfort & 4-Symptom Questionnaire
- VAS
- OSDI[©]
- BCVA Utilizing an ETDRS Chart
- Slit-Lamp Biomicroscopy
- Conjunctival Redness
- TFBUT

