10.4.7 Safety Variables

Adverse events will be coded using the MedDRA dictionary. Frequencies and percentages of subjects with treatment-emergent adverse events (TEAEs), serious TEAEs, and TEAEs causing premature discontinuation will be provided by treatment group. An AE is treatment emergent if it 1) occurs after the first dose of randomized study treatment or 2) if it is present prior to receipt of randomized study treatment but worsens in severity or increases in frequency after the first dose of randomized study treatment. Furthermore, frequencies will be given of subjects with TEAEs by system organ class and preferred term; by system organ class, preferred term and maximal severity; by system organ class, preferred term for treatment-related AEs; by system organ class and preferred term for SAEs; and by system organ class, preferred term, and day of onset. Separate analyses will be performed for ocular specific and all AEs (including systemic).

Other safety endpoints including visual acuity, slit-lamp biomicroscopy, dilated fundoscopy, and intraocular pressure will be summarized by treatment group and visit using descriptive statistics. Changes or shifts from baseline will also be summarized where appropriate. For assessments performed by eye, study eye and fellow eye will be summarized separately. In addition, shifts from baseline to worst on-treatment value for ocular safety assessments will be summarized. All safety endpoints will be assessed using the Safety population.

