3.1 General Study Design

This is a Phase 3, multicenter, randomized, prospective, double-masked, placebo-controlled, parallel-arm design. Subjects will be randomized to one of the following treatment arms at Visit 2 (Day 1) and will be instructed to follow a twice daily (BID) dosing regimen:

- Tanfanercept Ophthalmic Solution 0.25% (N~150)
- Placebo Ophthalmic Solution (N~150)

Approximately 300 subjects will be randomly assigned to one of two treatment groups (1:1) to receive either Tanfanercept Ophthalmic Solution 0.25% or Placebo Ophthalmic Solution as topical ophthalmic drops administered bilaterally twice daily (BID). The total number of expected participants, including screen failures, is approximately 857 subjects.

Information regarding subjects, Sponsor, Clinical Research Organizations, and site personnel will be masked and treatment group assignment will be unknown to subjects.

During the 14-day screening period, endpoint measurements will be taken to ascertain eligibility to enter the study. Those who qualify will be randomized to receive study drug in a double-masked fashion for 56 days. Subjects will self-administer drops BID.

Table 1 shows the scheduled study visits, planned study day (note that there is no Day 0 and that Day 1 corresponds to the day of randomization), the acceptable visit window for each study visit, and the analysis visit window.

Table 1. Scheduled Study Visits, Planned Study Days, and Visit Windows

Scheduled Visit	Planned Study Day	Visit Window	Analysis Visit Window
Visit 1	Day -14	± 2 days	Day -16 to Day -1
Visit 2	Day 1	N/A	N/A
Visit 3	Day 8	± 1 day	Day 2 to Day 11
Visit 4	Day 15	± 2 days	Day 12 to Day 21
Visit 5	Day 29	± 2 days	Day 22 to Day 43
Visit 6	Day 57	± 3 days	Day 44 to Day 60

Analysis visit windows will be implemented for efficacy analyses only. If a subject has multiple assessments/results reported within an analysis visit window, the following selection hierarchy will be implemented.

1. If results are reported at the planned study day and at an unscheduled visit, then the results reported on the planned study day will be selected.
2. If no results are reported on the planned study day, then the results/observation reported at the study day closest to the planned study day will be selected.

If there is a tie on the number of days prior to planned study day and post planned study day, then the results/observation reported prior to planned study day will be selected.

[figure not shown]

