15.1 Adverse Events

An AE is defined as any untoward medical occurrence associated with the use of IP in humans, whether or not considered IP-related. An AE can be any unfavorable and unintended sign (e.g., an abnormal laboratory finding), symptom, or disease temporally associated with the use of an IP, without any judgment about causality. An AE can arise from any use of the IP (e.g., off-label use, use in combination with another drug or medical device) and from any route of administration, formulation, or dose, including an overdose. All AEs will be coded using MedDRA Version 24.0.

Treatment-emergent adverse events (TEAEs) are defined as any event that occurs or worsens on or after the day that randomized study treatment is initiated.

An overall summary will be presented that includes the number of AEs, TEAEs, SAEs, treatment-emergent serious adverse events (TE-SAEs), number of subjects with TEAEs by maximum severity, and number of subjects with TEAEs by relationship to study drug. The summary will also include the number and percentage of subjects with treatment discontinuation due to an AE, the number and percentage of subjects with an AE resulting in death, and the number and percentage of subjects who experienced at least one AE, TEAE, SAE, and TE-SAE by treatment group and for all subjects. This summary will include breakdowns of AEs and TEAEs further categorized as ocular or non-ocular as well as the number and percentage of resolved ocular AEs and the mean and SD number of days until AE resolution for resolved ocular AEs.

Additional summaries of TEAEs will be provided showing the number and percentage of subjects who experienced at least one TEAE. These summaries will be presented by SOC and PT. Non-ocular TEAEs will be summarized using discrete summary statistics and presented by treatment group at the subject and event level by SOC and PT. Ocular TEAEs will be similarly summarized at the subject and event level by SOC and PT. If a subject reports the same PT multiple times within the same SOC, that PT will only be reported once within that SOC. As with the PT, if a subject reports multiple conditions within the same SOC, that SOC will only be reported once. In the summary, SOC will be listed in order of descending frequency for all subjects; PTs will be listed in order of descending frequency for all subjects within each SOC.

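### The SAP starts the treatment-emergent window on the calendar day of first dose, not after the first dose as the protocol requires, so Day 1 events that begin or worsen before dosing are counted as treatment-emergent

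*SAP*

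**What the plan says.** SAP section 15.1 sets the start of the window by date: a TEAE is "any event that occurs or worsens on or after the day that randomized study treatment is initiated".

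The protocol sets it by dose, in two places:

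- Synopsis, Safety Variables: "An AE is treatment emergent if it occurs or worsens after the first dose of study treatment".
- Section 10.4.7: an event qualifies if it "occurs after the first dose of randomized study treatment", or if it was already present and "worsens in severity or increases in frequency after the first dose of randomized study treatment".

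SAP section 1 says that its methods take precedence over the protocol's. SAP section 18 states that nothing has changed from the protocol's analyses.

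On timing, SAP section 3.1 says that "Day 1 corresponds to the day of randomization". Protocol section 8.4 says of the visit procedures: "Procedures listed below should be performed in the given order". The Visit 2 list in section 8.4.3 has this item near its start: "Monitoring and Query of AEs: Report any AEs that occur after signing the ICF". The examinations, randomization and blood sampling come next, then the dose: "Randomized subjects will self-administer their initial study drug dose bilaterally at the study site". A second adverse event query is listed after the dose.

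**The concern.** The two definitions differ over the hours of Day 1 that precede the first randomized dose. That period is not empty: both eyes are examined, stained with fluorescein and lissamine green and tested with Schirmer strips, and blood is drawn. These procedures can themselves produce irritation or similar events. Under the SAP such an event counts as treatment-emergent in the arm that the subject goes on to receive. It also enters the earliest onset category (before Day 9) in the tables by study day.

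An event that precedes the first dose cannot be an effect of the assigned drug. Counting it adds the same expected background to both arms and pulls a relative comparison toward no difference. The boundary governs every TEAE table, and a reader who relies on SAP section 18 would not know that it had moved.

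The SAP is also not consistent with itself. Section 8.3 takes the last measure before treatment starts, usually on Day 1, as baseline, and section 11.2 separates prior from concomitant medications at the first administration of randomized drug. Only the TEAE rule uses the calendar day.

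**Working it through.** The plan states no figure on this point, so there is none to reproduce. The check is a comparison of texts, followed by an illustration of size.

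**Step 1: which events change status.**

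| Event | Protocol 10.4.7 | SAP 15.1 |
|---|---|---|
| Onset in run-in, reported or still present at Visit 2, no worsening | Not a TEAE | Not a TEAE |
| Onset or worsening on Day 1, before the dose | Not a TEAE | TEAE |
| Onset or worsening on Day 1, after the dose | TEAE | TEAE |
| Onset or worsening from Day 2 | TEAE | TEAE |
| Present before the dose, more frequent afterwards, no more severe | TEAE | Not stated |

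The second row is the point at issue. The last row is a related gap: the SAP drops the protocol's criterion on frequency.

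**Step 2: order of Visit 2 (protocol 8.4.3).** Adverse event query; questionnaires; visual acuity; slit lamp; redness; tear film break-up time; fluorescein; lissamine green; Schirmer's test; eligibility review; randomization; blood draw; first dose; drop comfort; second adverse event query. All fall on Day 1, so the second row of the table describes real observation time.

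**Step 3: size, on assumed rates.** The documents give no adverse event rates. Assume true post-dose TEAE rates p of 10% (tanfanercept) and 5% (placebo), and a pre-dose Day 1 event rate q that is the same in both arms and independent of later events. The rate under the SAP rule is 1 − (1 − p)(1 − q). For q = 1%, this is 1 − 0.90 × 0.99 = 10.90% against 1 − 0.95 × 0.99 = 5.95%.

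| q | Tanfanercept | Placebo | Ratio | Difference (points) |
|---|---|---|---|---|
| 0% | 10.00% | 5.00% | 2.00 | 5.00 |
| 1% | 10.90% | 5.95% | 1.83 | 4.95 |
| 2% | 11.80% | 6.90% | 1.71 | 4.90 |
| 3% | 12.70% | 7.85% | 1.62 | 4.85 |

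Simple addition without overlap gives nearly the same ratios: 11/6 = 1.83, 12/7 = 1.71 and 13/8 = 1.63, with the difference fixed at 5 points.

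With the 130 subjects per arm in SAP section 5, the extra subjects with a TEAE number 130 × 0.90% = 1.2 (tanfanercept) and 130 × 0.95% = 1.2 (placebo) at q = 1%. At q = 3% they number 130 × 2.70% = 3.5 and 130 × 2.85% = 3.7. That is about 1 to 4 subjects per arm.

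**The case against.** The best defense is practical. Protocol section 9.1 lists the date of onset among the items to document for an adverse event, and no clock time. With dates alone, the order of a Day 1 event and the dose cannot be derived, and counting the whole day is an inclusive convention that loses no true post-dose event. This stands as a reason for a default when timing is unknown. It does not justify applying the rule where the order is known, or leaving it undeclared. The SAP gives no such reason.

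The consequences are also limited. SAP section 15.1 plans counts and percentages of TEAEs without a between-arm test. Separate tables show treatment-related TEAEs, and an event clearly due to another known cause, or arising before exposure, is classed as not related and stays out of them. Drop comfort after dosing is compared directly by t-test (SAP 16.1.1). An investigator can also decline, under exclusion 14, to randomize a subject with a troublesome pre-dose event. All of this stands and keeps the point small.

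Two stronger readings are tempting, and the documents do not support them:

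- A reader might infer that everything reported at the first Visit 2 query becomes treatment-emergent. The SAP rule depends on when an event occurs or worsens, not on when it is reported. A run-in event that is merely reported or still present that morning is unaffected.
- A reader might infer that the rule hides a local-tolerance signal. The ratio is diluted, but the risk difference barely changes, and the related-event tables and drop comfort data remain.

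**Conclusion.** The conflict is real and undeclared. As written, SAP section 15.1 counts as TEAEs those events that start or worsen on Day 1 before dosing, and protocol section 10.4.7 excludes them. The effect is a modest inflation of both arms, balanced in expectation, so it does not favor either arm.

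On the assumed 10% and 5% rates, with 1 to 3 points of pre-dose events, the ratio falls from 2.0 to between about 1.8 and 1.6. The risk difference goes from 5.0 to between 4.95 and 4.85 points. Both sets of rates are assumptions, and the true size cannot be derived from the documents. The text conflict is certain; the practical harm is probably small. Severity: minor.

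**What to change.** 1. In SAP section 15.1, restore the whole protocol 10.4.7 definition: onset after the first dose of randomized treatment, or a pre-existing event that becomes more severe or more frequent after that dose. Restoring onset and worsening alone would leave the two documents in disagreement on frequency.
2. Before unmasking, classify each event with onset or worsening on Day 1 as before or after dosing. Events captured at the first Visit 2 query are before dosing. Those first captured at the second query may have arisen during the procedures or after the dose, so they need source records or a site query.
3. Count as a TEAE any Day 1 event that cannot be placed before dosing. This keeps the conservative default.
4. If the day rule is kept for untimed events, declare it in SAP section 18 with the reason.

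The cost is a revised SAP definition and a small number of retrospective site queries. A new case report form field would come too late for most subjects, because SAP section 5 shows that 260 had already been randomized. The work must therefore rely on existing records.

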9 ADVERSE EVENTS

9.1 Adverse Events

An AE is defined as any untoward medical occurrence associated with the use of an IP in humans, whether or not considered IP-related. An AE can be any unfavorable and unintended sign (e.g., an abnormal laboratory finding), symptom, or disease temporally associated with the use of an IP, without any judgment about causality. An AE can arise from any use of the IP (e.g., off-label use, use in combination with another drug or medical device) and from any route of administration, formulation, or dose, including an overdose. An AE can arise from any delivery, implantation, or use of a medical device, including medical device failure, subject characteristics that may impact medical device performance (e.g., anatomical limitations), and therapeutic parameters (e.g., energy applied, sizing, dose release) associated with medical device.

All AEs spontaneously reported by the subject and/or in response to an open question from study personnel or revealed by observation, physical examination or other diagnostic procedures will be recorded in the source document and on the appropriate pages of the eCRF. Any clinically relevant deterioration in clinical finding is considered an AE and must be recorded. When possible, signs and symptoms indicating a common underlying pathology should be noted as 1 comprehensive event.

Documentation regarding the AE should be made as to the nature, date of onset, end date, severity, relationship to IP, action(s) taken, expectedness, seriousness, and outcome of any sign or symptom observed by the physician or reported by the subject upon indirect questioning.

If a female has a positive pregnancy test during the study, the investigator will notify Ora immediately (within 24 hours) via the Pregnancy Report Form and also report on the appropriate eCRF. Any subject found to be pregnant during the course of the study shall be discontinued from the study. The investigator shall request from the subject and/or the subject's physician copies of all related medical reports during the pregnancy and shall follow and document medical findings throughout the pregnancy through to the outcome of the pregnancy. The investigator will retain these reports together with the subject's source documents and will provide a copy of all documentation to Ora.

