9.5 Type and Duration of the Follow-up of Subjects after Adverse Events

The investigator will follow unresolved AEs to resolution until the subject is lost to follow-up or until the AE is otherwise classified. Resolution means the subject has returned to baseline state of health or the Investigator does not expect any further improvement or worsening of the AE. If the subject is lost to follow-up, the Investigator should make 3 reasonable attempts to contact the subject via telephone, post, or certified mail. All follow-up attempts will be recorded in the subject's source document. Non-serious AEs identified on the last scheduled contact must be recorded on the AE eCRF with the status noted.

If the Investigator becomes aware of any new information regarding an existing SAE (i.e., resolution, change in condition, or new treatment), a new SAE/Unanticipated Report Form must be completed and faxed to Ora within 24 hours of the site's awareness of the new information. The original SAE form is not to be altered. The report should describe whether the event has resolved or continues and how the event was treated.

Any unresolved AEs or SAEs upon completion of the subject's last study visit will be followed for up to 30 calendar days by the study staff until the event or its sequelae resolve or stabilize at a level acceptable to the study physician. In addition, any newly identified AEs or SAEs determined to be potentially related to study IP or procedures after the subject's exit visit will be followed for up to 30 calendar days by the site staff until the event or its sequelae resolve or stabilizes at a level acceptable to the study physician, subject withdraws consent, or no further information can reasonably be gathered.

The investigator shall follow all pregnancies and document medical findings throughout the pregnancy through to the outcome of the pregnancy. The investigator will retain reports together with the subject's source documents and will provide a copy of all documentation to Ora.

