 - *Definite:* Relationship exists when the AE follows a reasonable sequence from the time of IP administration, follows a known response pattern of the drug class, is confirmed by improvement on stopping the IP and no other reasonable cause exists.
 - *Probable:* Relationship exists when the AE follows a reasonable sequence from the time of IP administration, follows a known response pattern of the drug class, is confirmed by improvement on stopping the IP and the suspect IP is the most likely of all causes.
 - *Possible:* Relationship exists when the AE follows a reasonable sequence from the time of administration, but could also have been produced by the subject's clinical state or by other drugs administered to the subject.
- **Not Suspected:** A reasonable possibility does not exist that the IP caused the AE. A not suspected AE can further be defined as:
 - *Not Related:* Concurrent illness, concurrent medication, or other known cause is clearly responsible for the AE, the administration of the IP and the occurrence of the AE are not reasonably related in time, OR exposure to IP has not occurred.

All possible, probable, and definite TEAEs are considered as treatment-related TEAEs.

All AEs will be presented in a subject listing for all screened subjects. Separate listings will be produced for Conjunctivitis AEs, SAEs, AEs leading to treatment discontinuation, and AEs leading to death for all randomized subjects.

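### The ocular AE duration row averages resolved events only, so it understates long durations and compresses arm differences; a Kaplan-Meier row should be added beside it

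*SAP*

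**What the plan says.** SAP section 15.1 describes an overall adverse event summary giving the subjects "who experienced at least one AE, TEAE, SAE, and TE-SAE by treatment group and for all subjects". For ocular events it adds two items in one sentence. The first is a count: "as well as the number and percentage of resolved ocular AEs". The second is a duration: "the mean and SD number of days until AE resolution for resolved ocular AEs". Neither the SAP nor the protocol plans a Kaplan-Meier curve, a median, or any other duration estimate that keeps unresolved events.

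Protocol section 9.5 has three statements that bear on this:

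- It opens with a general rule that the investigator follows unresolved events to resolution, until the subject is lost to follow-up or the event is otherwise classified.
- It then sets a limit: "Any unresolved AEs or SAEs upon completion of the subject's last study visit will be followed for up to 30 calendar days".
- It defines resolution as return to the baseline state of health, or as the investigator expecting no further change in either direction.

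Protocol section 9.1 requires the dates: "Documentation regarding the AE should be made as to the nature, date of onset, end date, severity, relationship to IP". For events open at the end, section 9.5 says: "Non-serious AEs identified on the last scheduled contact must be recorded on the AE eCRF with the status noted".

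**The concern.** An event still open at the end of follow-up is known to have lasted at least as long as it was observed. Leaving it out discards that information and removes the longest durations selectively. The resulting mean cannot exceed the follow-up window, and the arm with the longer events loses more of them. For a topical product, how long ocular events last is part of the tolerability picture, and this row is the planned summary of it. If the two arms differ in duration, the row will show less of the difference than exists. The resolved percentage signals that something has been left out, but a reader cannot recover the true durations from it.

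**Working it through.** The documents give no duration, resolution rate or resolution time, so there is no figure of the plan's own to reproduce. The check asks how far a resolved-only mean can depart from the truth under a simple model.

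**Inputs from the documents.** Study drug is given for 56 days; SAP section 3.1 has subjects "randomized to receive study drug in a double-masked fashion for 56 days". Protocol section 9.5 adds up to 30 days after the last visit, so the longest explicit horizon is 56 + 30 = Day 86.

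**Assumptions, not from the documents.** Onset is uniform over the 56 days. Durations are exponential with mean m.

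**Formulas.** An event has a remaining window W, uniform from a to b. With the 30-day extension a = 30 and b = 86; if follow-up ends at the last visit, a = 0 and b = 56.

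- Unresolved share: U = (m/56) × [exp(−a/m) − exp(−b/m)]
- V = (m/56) × [(a+m) exp(−a/m) − (b+m) exp(−b/m)]
- Resolved share: 1 − U
- Resolved-only mean: (m − mU − V) / (1 − U)

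**m = 20, follow-up to Day 86.** U = (20/56) × (0.2231 − 0.0136) = 0.0748, and V = 3.471. The resolved share is 92.5%. The mean shown is (20 − 1.497 − 3.471)/0.9252 = 16.2 days.

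**m = 60, follow-up to Day 86.** U = (60/56) × (0.6065 − 0.2385) = 0.3943, and V = 21.177. The resolved share is 60.6%. The mean shown is (60 − 23.658 − 21.177)/0.6057 = 25.0 days.

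A true ratio of 3.0 therefore appears as 25.0/16.2 = 1.5. The same formulas give:

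| True mean (days) | To Day 86: mean shown (resolved) | To last visit: mean shown (resolved) |
|---|---|---|
| 7 | 6.9 (99.8%) | 6.0 (87.5%) |
| 14 | 12.7 (97.1%) | 9.8 (75.5%) |
| 20 | 16.2 (92.5%) | 11.7 (66.5%) |
| 28 | 19.4 (85.2%) | 13.4 (56.8%) |
| 56 | 24.6 (63.0%) | 15.8 (36.8%) |
| 60 | 25.0 (60.6%) | 16.0 (35.0%) |

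A true twofold difference (14 v 28, or 28 v 56) appears as 1.5 or 1.3 with the 30-day extension, and as 1.4 or 1.2 without it. Simulation with 2,000,000 events per scenario agrees with these values to within rounding and simulation error.

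**Events that never resolve.** Suppose 40% of one arm's events never resolve, the rest average 7 days, and every event in the other arm averages 7 days. With follow-up to Day 86 the mean is 6.9 days in both arms. The resolved percentages are 59.9% and 99.8%, so here the percentage shows the whole difference and the mean shows none.

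**What a censored estimate targets.** For exponential durations the median is m × ln 2: 13.9 days for m = 20 and 41.6 for m = 60, so the ratio of 3.0 is preserved. In the 40% example the median solves 0.6 × (1 − exp(−t/7)) = 0.5, giving t = 7 × ln 6 = 12.5 days, against 7 × ln 2 = 4.9 in the other arm.

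**The case against.** A reader might infer that persistent events vanish from the safety summary and that an arm with longer-lasting events could look almost as good as the other. The documents do not support that. The resolved percentage stands in the same sentence, and its complement is the unresolved share. In the 20 v 60 example the table would show 93% v 61% resolved beside 16 v 25 days, and nobody would read those arms as alike. Maximum severity and discontinuations due to AEs are in the same summary, and section 15.1 adds: "All AEs will be presented in a subject listing for all screened subjects". The row's label also states its denominator, so it misreports nothing.

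Three further objections have weight:

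- **Resolution is defined broadly.** Under Protocol section 9.5 a persistent but stable event can count as resolved. If the recorded outcome follows that definition, such events stay in the mean. The documents do not say whether it does.
- **The follow-up limit is not clear-cut.** Section 9.5 contains both a follow-to-resolution rule and a 30-day limit, so Day 86 is one reading.
- **The size depends on assumed durations.** The 60-day example is longer than the treatment period itself. For true means of 7 to 14 days with the 30-day extension, the row is nearly right or modestly low.

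These points limit the concern but do not remove it. Where events are long, a reader of 16 v 25 days with 93% v 61% resolved can see that persistence differs but cannot get back to 20 v 60.

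**Conclusion.** The concern holds as a limitation of one descriptive row. The resolved-only mean is biased low, more so in the arm with longer events, and no planned output corrects it. The size ranges from negligible (7 days shown as 6.9) to a threefold difference shown as about 1.5-fold, under uniform onset, exponential durations and follow-up to Day 86. It is larger if follow-up in the database ends at the last visit. No test, decision rule or efficacy claim depends on the row, and the resolved percentage already warns the reader. That makes this a cheap improvement and not a flaw in the safety analysis. It does not justify removing the labelled mean.

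**What to change.** Keep the number and percentage resolved and the resolved-only mean and SD, labelled as now. Add to Table 14.3.1.1, by arm, the Kaplan-Meier median of days to resolution for ocular TEAEs, with quartiles where they are reached. State in SAP section 15.1:

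- that resolution follows the definition in Protocol section 9.5;
- that unresolved events are censored at the last recorded AE follow-up or the study exit date. One horizon should apply to all events: if end dates after exit are used, follow-up dates after exit are needed for unresolved events too. Otherwise every event should be cut at exit;
- that the new row uses TEAEs while the existing rows use all ocular AEs. AEs are collected from consent, so the existing rows can include events from the open-label placebo run-in.

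The cost is one more descriptive row. Onset and end dates are already recorded, and SAP section 12.2 already uses the study completion or discontinuation date. The documents do not show that AE follow-up dates after exit are in the eCRF; Protocol section 9.5 places attempts to contact lost subjects in the source document.

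The row needs three caveats. Censoring may be informative, because follow-up can stop once an event has stabilised or when a subject withdraws. A subject may contribute several events, so events are not independent. The median may not be reached if few events resolve, which is a further reason to keep the resolved percentage beside it.
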